6.3 Measures to Minimize Bias: Randomization and Blinding

Eligible patients will be randomized in a ratio of 1:1:1:1 to one of the following treatment groups: naldemedine 1.25 mg, 2.5 mg, or 5 mg or placebo. Randomization will be stratified by the planned surgical procedure, ie, small bowel resection with primary anastomosis, large bowel resection with primary anastomosis, or radical cystectomy requiring bowel transection with primary anastomosis. All patients will be centrally randomized to study treatment using an Interactive Web Response System (IWRS). Before each site is initiated, the login information and directions for the IWRS will be provided.

The IWRS will be programmed with blind-breaking instructions. In case of an emergency, the investigator has the sole responsibility for determining if unblinding of a patient's treatment assignment is warranted. Patient safety must always be the first consideration in making such a determination. If the investigator decides that unblinding is warranted, the investigator should make every effort to contact the contract research organization (CRO) prior to unblinding unless this could delay emergency treatment of the patient. If a patient's treatment assignment is unblinded, the CRO must be notified within 24 hours after breaking the blind, and the treatment assignment should not be disclosed to the CRO. The date and reason that the blind was broken must be recorded in the source documentation and the IWRS.

6.4 Study Treatment Compliance

The investigator or qualified study personnel will administer study treatment to each patient and will observe the patient for compliance with taking the study treatment. Study treatment administration will be recorded in the electronic case report form (eCRF). In addition, if the patient refuses study treatment or if he or she vomits within 1 hour of dosing, this information will also be recorded in the eCRF.

6.5 Medical History and Prior and Concomitant Therapy

Any prior history of postoperative ileus and postoperative gastrointestinal dysfunction must be recorded on the eCRF as part of the patient's medical history.

Any medication or vaccine (including over-the-counter or prescription medicines, vitamins, and herbal supplements) that the patient is receiving at the time of enrollment or receives during the study must be recorded in the eCRF along with the following information:

- Reason for use
- Dates of administration including start and end dates
- Dosage information including dose, route of administration, and frequency

The preoperative bowel preparation, if any, must be recorded in the eCRF. Additionally, the total volume of intravenous fluids administered during the surgery must be recorded in the eCRF.

The CRO's medical monitor should be contacted if there are any questions regarding permissible prior or concomitant therapy.

In addition to the prior and concomitant therapy exclusions in [Section 5.2](#), the following medications are prohibited for 14 days before the first dose of study treatment and through the end of study treatment:

- Strong cytochrome P450 3A (CYP3A) inducers (eg, carbamazepine, enzalutamide, mitotane, phenytoin, rifampin, St. John's Wort) (see [Appendix 6](#))
- Strong CYP3A and P-glycoprotein (P-gp) inhibitors (eg, clarithromycin, diltiazem, grapefruit juice, indinavir, ketoconazole, ritonavir) (see [Appendix 7](#))
- Other opioid antagonists
- Prophylactic use of laxatives (eg, magnesium citrate, magnesium hydroxide, magnesium sulfate, castor oil, sodium phosphate, sodium biphosphate, polyethylene glycol enemas, and stimulant laxatives, including bisacodyl); however, if needed, laxatives may be used for rescue therapy

Re-insertion of the nasogastric tube is permitted if needed (see [Section 8.1.2.2](#)).

The following elements of the enhanced recovery protocol at the study site must be recorded as yes or no in the eCRF at Baseline (planned) and at the day of discharge or early termination (actual):

- Three elements required by the protocol:
 - Early removal of the nasogastric tube, defined as removal of the nasogastric tube at the end of surgery
 - Early ambulation, defined as ambulation on Day 1
 - Early diet advancement on Day 1
- Four other elements that may be used at the study site:
 - Antibiotic prophylaxis
 - Preoperative carbohydrate drink
 - Epidural anesthesia in addition to general anesthesia
 - Chewing gum postoperatively

The investigator must determine appropriate management and treatment of the patient, as clinically indicated, in the event of signs or symptoms of any of the following:

- Opioid withdrawal; if opioid withdrawal is suspected, the patient should be monitored
- Severe hypersensitivity thought to be related to study treatment
- Gastrointestinal perforation

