- j To be measured once daily as close as possible after waking; vital signs include systolic/diastolic blood pressure (assessed after approximately 3 to 5 minutes of rest), and pulse rate.
- k To be performed any time from 14 days to day of surgery (Day -14 to Day 0, respectively). An electrocardiogram obtained within 2 weeks prior to the patient signing the informed consent form that shows no clinically significant abnormal finding may be used.
- l To be assessed once daily in the morning at approximately the same time of day; baseline is defined as the pain assessment on the morning of Day 1.
- m Hematology (platelet count, erythrocytes [red blood cell count], hemoglobin, hematocrit, leukocytes [white blood cell count with differential: neutrophil count, lymphocyte count, monocyte count, eosinophil count, basophil count]), clinical chemistry (blood urea nitrogen, creatinine, chloride, potassium, sodium, calcium, aspartate aminotransferase, alanine aminotransferase, alkaline phosphatase, total bilirubin, international normalized ratio, total protein, and albumin).
- n Required for female patients of childbearing potential (that is, not surgically sterile by hysterectomy, bilateral oophorectomy, and/or bilateral salpingectomy or tubal ligation with appropriate documentation of such surgery *OR* not postmenopausal [defined as at least 12 months of spontaneous amenorrhea in a woman > 45 years of age]). If the urine pregnancy test is obtained prior to Day -1 and is negative, the test must be repeated on Day -1 or Day 0. Additional pregnancy testing is not required during the treatment period unless clinically indicated.
- o The actual date and time (24-hour clock) of all study treatment dosing and each meal prior to dosing will be recorded in the eCRF.
- p First dose is to be administered 30 minutes to 6 hours prior to the scheduled start of surgery on the operative day (Day 0).

- q A second dose will be administered postoperatively the evening of the operative day (Day 0).

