9.4.5.1 Primary Efficacy Endpoint

The primary endpoint will be time from the end of surgery (defined as the time the patient leaves the operating room) to time to first toleration of solid food (defined as the time when the patient consumes a meal that requires chewing and has no significant nausea or vomiting, as per the judgment of the investigator, for 4 hours after that solid food) and first bowel movement (GI2).

The mean survival time, which is also referred to as the RMST, of GI2 events within 240 hours will be estimated using the area under the Kaplan-Meier (KM) curve. To demonstrate the linear dose-response relationship between treatment groups (3 naldemedine groups and placebo group) and the RMST, the linear contrast test for trend with contrast coefficients of (-3, -1, 1, 3) will be performed. If a dose-response relationship is detected, then pairwise comparisons of the RMST between each dose group of naldemedine and the placebo group will be conducted, and the treatment differences (with its 95% confidence interval [CI]) will be provided. If an event does not occur during the evaluation period of 240 hours, the patient will be censored at the time of his/her last nonmissing postbaseline assessment. The same analysis will be performed in the Per Protocol set. In addition, the reason for discharge prior to having the first bowel movement will be listed.

Patients will continue to be evaluated for efficacy regardless of treatment adherence. The use of additional therapies or interventions that could treat any component of the primary endpoint (eg, motility agents, anti-emetics, laxatives, etc), may confound the results of the primary efficacy analysis. This list of therapies will be finalized before database lock. To examine this issue, the following exploratory analyses of the GI2 endpoint will be performed or provided:

- Repeat of the primary analysis, excluding all patients who received additional therapies at any time postrandomization that could treat any of the components of the GI2 endpoint. It is recognized that this subset is selected based on postrandomization decisions, may be confounded with the treatment group, and may not represent a randomized subgroup of the primary endpoint.
- Table of proportion of patients in each treatment group who received additional therapies that could treat any of the GI2 components.

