- Two-way table summarizing each patient's status at the end of the trial regarding receipt of an additional therapy that could treat any of the GI2 components and whether the GI2 endpoint was achieved. For example, the rows can be yes/no for GI2 endpoint achieved, and the columns can be receipt of additional therapy. This

table will be done during the evaluation period of 240 hours for patients and by treatment group.

- Proportion of patients in each group that achieve the GI2 endpoint, regardless of use of additional therapies that could treat any of the GI2 components. This will be tabulated cumulatively by day. The cumulative proportions achieving the GI2 endpoint will be compared at Day 10 with the difference in proportions and an associated 95% CI will be provided.
- Proportion of patients in each group that achieve the GI2 endpoint, where the use of additional therapies that could treat any of the GI2 components included in the analysis as a patient failure to achieve the GI2 endpoint, beginning with the day the patient first receives the additional therapy. This will be tabulated cumulatively by day. The cumulative proportions achieving the GI2 endpoint will be compared at Day 10, with the difference in proportions and an associated 95% CI provided.

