### 9.1 Primary Endpoint

The time from the end of surgery (defined as the time the patient leaves the operating room) to time to first toleration of solid food (defined as the time when the patient consumes a meal that requires chewing and has no significant nausea or vomiting, as per the judgment of the investigator, for 4 hours after that solid food) and first bowel movement (GI2) will be the primary endpoint and called "Time to event of GI2". The time to event of GI2 will be the later time at which all of the following criteria are met:

- First toleration of solid food (as defined above)
- First bowel movement after surgery

If one of three time components (end of surgery time, time when the patient first tolerates solid food, and time of first bowel movement) is missing, time to event of GI2 will be considered as missing.

If time to event of GI2 does not occur during the evaluation period of 240 hours, the patient will be censored at the time of his/her last nonmissing postbaseline assessment.

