### 9.1.2 Supplementary Analysis

The following supplementary analyses will be undertaken using the mITT population, unless otherwise noted:

- Repeat of the primary endpoint analysis, based on the PPS.
- Repeat of the primary endpoint analysis, excluding all patients who received additional therapies that could impact the primary endpoint at any time until the

---

day GI2 is achieved or Day 10 or withdrawal or discharge day, whichever comes first. The list of all patients who received additional therapies that could impact the primary endpoint at any time until achievement of the GI2 endpoint or completion of the study will be provided by the Shionogi Medical Monitor prior to database lock and unblinding.

- For each treatment group, a two-way table summarizing the proportion of patients by achievement of GI2 until 240 hours (yes/no) and additional therapies received that could impact the primary endpoint at any time (yes/no) until Day 10 or withdrawal or discharge day, whichever comes first.
- Proportion of patients achieving GI2 by treatment group and cumulative day. As for the definition of cumulative day, if patients achieved GI2 on a certain day, GI2 will be considered as sustained through Day 10 or withdrawal or discharge day, whichever comes first (called “last day”). Pairwise comparison as Cochran Mantel Haenszel test adjusted by surgical procedure will be applied to the proportion at Day 10.
- Proportion of patients achieving GI2 by treatment group, surgical procedure, and cumulative day.

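### Therapy given on the day of GI2 cannot be ordered against GI2 from the fields listed in Protocol 6.5, so the SAP 9.1.2 exclusion analysis can misclassify those patients

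*Protocol*

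**What the plan says.** **Data capture.** For concomitant medication, Protocol 6.5 asks for the reason for use, "Dates of administration including start and end dates" and "Dosage information including dose, route of administration, and frequency". No clock time is listed. Where the protocol wants clock time it says so, as in footnote o of the Schedule of Activities: "The actual date and time (24-hour clock) of all study treatment dosing and each meal prior to dosing will be recorded in the eCRF".

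**Endpoint.** GI2 is measured in hours up to 240. SAP 9.1 states: "The time to event of GI2 will be the later time at which all of the following criteria are met". The two criteria are toleration of solid food and first bowel movement. Toleration is timed at a chewed meal and requires no significant nausea or vomiting for the next 4 hours.

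**Analyses with a cut near GI2.**
- SAP 9.1.2 excludes patients who had additional therapy up to the "day GI2 is achieved or Day 10 or withdrawal or discharge day, whichever comes first". SAP 6.5.1 starts each study day at midnight, so this is a calendar day.
- The next sentence of that bullet describes the Medical Monitor's list of such patients, with therapy "at any time until achievement of the GI2 endpoint or completion of the study will be provided".
- Protocol 9.4.5.1 also has an analysis that counts additional therapy as failure, "beginning with the day the patient first receives the additional therapy".

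**The concern.** Protocol 9.4.5.1 itself warns that laxatives, anti-emetics and motility agents may confound the primary result, and Protocol 6.5 allows laxatives as rescue. The additional-therapy analyses are the plan's answer to that warning, so they need to separate therapy that could have contributed to GI2 from therapy that could not.

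On the GI2 day the listed fields do not allow this, and SAP 9.1.2 does not say whether that day is inside the window. Two patients show the consequence:
- Unaided GI2 at 09:00, laxative at 18:00. If the GI2 day counts, this patient is excluded although the laxative could not have affected GI2.
- Laxative at 09:00, bowel movement and GI2 at 15:00. If the GI2 day does not count, this patient stays in as unaided.

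Therapy soon after GI2 is plausible. Study treatment ends by reference to the date GI2 is met, and the bar on prophylactic laxatives runs only through the end of study treatment.

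**Working it through.** The plan states no figure on this point, so there is none to reproduce. The check has three steps.

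**1. Which analyses need the order of therapy and GI2 within a day?**

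| Analysis | Therapy window | Within-day order needed? |
|---|---|---|
| Primary analysis | Therapy not used | No |
| Protocol 9.4.5.1 exclusion, "excluding all patients who received additional therapies at any time postrandomization that could treat any of the components of the GI2 endpoint" | Any time after randomization | No |
| Protocol table of proportion receiving therapy | No cut at GI2 | No |
| Two-way table, GI2 by therapy | 240 hours (protocol); Day 10, withdrawal or discharge (SAP) | No |
| GI2 proportion regardless of therapy | Therapy not used | No |
| SAP 9.1.2 exclusion | To the GI2 day; list to achievement of GI2 | Yes |
| Protocol therapy-as-failure | From the day of first therapy | Depends on reading |

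Therapy-as-failure can be read in two ways. Literally, a treated patient is a failure from that day on even if GI2 came earlier. Order then does not change the Day 10 result, and the rule itself is what fails a patient treated only after GI2. If instead an earlier GI2 is meant to stand, order on the GI2 day decides the outcome and the listed fields cannot supply it. SAP 9.1.2 does not carry this analysis forward.

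**2. How many patients could be misclassified in the SAP exclusion analysis?**

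Inputs:
- n = 44 or 85 per group in the mITT Population (Protocol 9.2).
- r = share of patients whose only additional therapy is on the GI2 day. Not in the documents; assumed 2% to 20%.
- f = share of those who received it after GI2. Not in the documents; 0.5 if both clock times are independent with the same distribution (simulation gave 0.500), range 0.25 to 0.75.

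If the GI2 day counts, wrongly excluded = n × r × f. If it does not, wrongly kept as unaided = n × r × (1 − f). At f = 0.5 the two are equal, and over 0.25 to 0.75 they span the same range.

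| r | n = 44, f = 0.5 | n = 85, f = 0.5 |
|---|---|---|
| 2% | 0.4 | 0.8 |
| 5% | 1.1 | 2.1 |
| 10% | 2.2 | 4.2 |
| 20% | 4.4 | 8.5 |

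Over f = 0.25 to 0.75 the range is 0.2 to 6.6 patients at n = 44 (44 × 0.02 × 0.25 to 44 × 0.20 × 0.75) and 0.4 to 12.8 at n = 85.

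**3. How often would an aided bowel movement share the date of the therapy?**

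Assume therapy is given uniformly between 08:00 and 20:00, with an exponential delay of mean m hours to the bowel movement. Time left to midnight is then uniform on 4 to 16 hours, and the same-date share is 1 − (m/12)(e^(−4/m) − e^(−16/m)).
- m = 6: 0.778
- m = 12: 0.547
- m = 24: 0.334

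These are shares of aided bowel movements under assumed delays, not shares of trial patients. They matter only if the GI2 day is left out of the window. GI2 may also fall later than the bowel movement, because it waits for food toleration.

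**The case against.** A reader might infer that all the additional-therapy analyses are compromised, or that the primary result is. The documents do not support either. The primary analysis follows patients whatever they receive, and most of the other analyses never order therapy against GI2. The affected rules are also written by day, so they can be run on dates as they stand.

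The case for leaving things alone has four further parts.
- **The eCRF is not among the documents.** The list in 6.5 is not called exhaustive. SAP 9.3.4 computes nasogastric tube duration in hours to two decimals, although the protocol's schedule does not list those clock times. Source records include hospital charts and pharmacy dispensing records. This stands: date-only capture is inferred from 6.5, and times may exist.
- **The Medical Monitor settles the list before unblinding.** This protects against choices made with knowledge of treatment. It does not supply the order of events, and the plan does not say that times will be consulted. The list's cut also differs from the analysis it feeds.
- **A day-level rule that includes the GI2 day has one merit.** If the bowel movement came first, an anti-emetic given 2 hours after the qualifying meal falls after the recorded GI2 time but inside the 4 hours that define toleration. A single cut at the GI2 time would call that recovery unaided. This stands and shapes the fix.
- **These analyses are exploratory or supplementary.** The protocol already concedes that the untreated subset is selected after randomization. That is correct, and clock times would not cure it.

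**Conclusion.** From the fields listed in Protocol 6.5, therapy on the GI2 day cannot be ordered against GI2. SAP 9.1.2 uses two different cuts in one bullet and leaves the status of that day open. Its exclusion analysis can therefore drop patients treated only after GI2 or keep same-day aided recoveries as unaided. The protocol's therapy-as-failure analysis has a related weakness if it is kept. No other analysis is touched.

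The size cannot be derived from the documents. The illustration of 0.4 to 8.5 patients per group rests on assumed values of r and f. It might also be inferred that the faster-recovering arm is distorted. That is possible, but nothing in the documents gives its direction or amount.

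The problem comes from a day-level rule combined with date-level data. Recording times without moving the cut would not resolve it. The change is worth making because it is cheap and these analyses are the plan's response to a confounder it names itself.

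**What to change.** 1. **Protocol 6.5.** For drugs on the additional-therapy list, record start date and 24-hour clock time from the end of surgery until GI2 or 240 hours. For anti-emetics, continue to the end of the 4-hour toleration window where that is later than GI2. If the eCRF already captures times, only the SAP needs to change.
2. **SAP 9.1.2, cut.** Count a laxative or motility agent only if it started before the GI2 time. Count an anti-emetic if it started before the end of the 4-hour window after the qualifying meal.
3. **SAP 9.1.2, missing times.** Treat a same-day therapy with no recorded time as preceding GI2.
4. **Medical Monitor's list.** Use the same cut as the analysis, and the same end of window for patients who do not reach GI2.
5. **Therapy-as-failure analysis.** State whether it is retained. If so, say whether GI2 reached before the therapy still counts as achieved, and apply the same cut.

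Cost: one time field for a short drug list and a small change to one derivation. The downside is slightly more data entry, and times after discharge will be patient-reported.

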6.6 Dose Modification of Study Treatment

Dose modification of study treatment is not permitted in the study.

6.7 Treatment after the End of the Study

Study treatment will not be administered after the end of the study.

7. DISCONTINUATION OF STUDY TREATMENT AND PATIENT DISCONTINUATION/WITHDRAWAL

7.1 Discontinuation of Study Treatment

A patient may discontinue study treatment prior to Day 10 if he or she meets the primary endpoint, GI2, or on the date on which the discharge order is written, whichever occurs first. Discontinuation of study treatment for any other reason will be determined by the investigator if he or she believes that it is in best interest of the patient. Female patients who become pregnant during the study will be followed as described in [Section 7.2](#), [Section 8.3.5](#), and [Appendix 4](#). The investigator will withdraw a patient from study treatment based on the management and discontinuation criteria for abnormal liver function tests ([Appendix 5](#)). The investigator should consider discontinuation of study treatment if opioid withdrawal is suspected on any assessment day. In addition, discontinuation of study treatment is required if:

- The patient has an unplanned ileostomy or colostomy during the surgical procedure.
- A patient has a score > 36 on the Clinical Opiate Withdrawal Scale (COWS) on any assessment day
- Hypersensitivity thought to be related to study treatment occurs and is considered severe in intensity, as assessed by the investigator
- There is any sign or symptom suggestive of gastrointestinal perforation, as assessed by the investigator

See the SoA for data to be collected at the time of treatment discontinuation (eg, at the Early Termination Visit).

